13.0 Data Disclosure and Patient Confidentiality – 40 –

14.0 Ethical Considerations – 40 –

14.1 Protection of Human Subjects from Research Risks

14.2 Institutional Review Board

14.3 Informed Consent

References - 42 -

PROTOCOL SUMMARY

Protocol Number:

Protocol Title: An open-label, single institution phase II study using radioactive yttrium⁹⁰ microsphere (SIR-Spheres[®]) in uveal melanoma patients with hepatic metastasis

Study Objectives:

Primary objectives

- (1) Investigate the potential efficacy (clinical response) of radioactive yttrium⁹⁰ microsphere in hepatic metastasis from uveal melanoma.
- (2) Investigate the safety of radioactive yttrium⁹⁰ microsphere in patients with metastatic uveal melanoma.

Investigate correlation between molecular characteristics of metastatic uveal melanoma and treatment outcomes.

Secondary objectives:

Investigate overall survival, progression free survival, and duration of response

Study Population: Patients with stage IV uveal melanoma with hepatic metastasis

Study Design: Single institution phase II study.

Investigational Product: Radioactive yttrium⁹⁰ microsphere (SIR-Spheres[®] microspheres)

Dosage Form: Liquid suspension

Route of Administration:	Intrahepatic arterial infusion
Dosage and Treatment:	Up to 3.0 Giga-Becquerels (GBq) for two treatments
Endpoints:	Response Rate: 60% stabilization rate (CR+ PR+SD) warrants future study. Adverse Events: Treatment-emergent and related serious adverse events, and Grade 3 and 4 laboratory abnormalities for safety assessments
Other Parameters:	Overall survival (OS), progression free survival (PFS) and duration of response in the liver
Duration of Subject Participation in Study:	Maximum of 2 years after the last radiosphere treatment or death, or study closure
Duration of Follow-up:	Safety data will be collected for three months after the last radiosphere treatment, or initiation of a different type of locoregional or systemic treatment for progression of disease, or death, whichever comes first. Survival information will be collected via phone or visit on a quarterly basis up to 2 years after the last radiosphere treatment or death.
Number of Subjects:	48
Required	

SIR-Spheres Microspheres Clinical Treatment Plan

Events	Screening Evaluation	Enrollement	Tumor biopsy	Flow Study	Pretreatment assessment	Initial Treatment	Post-Treatment	Second Treatment (*5)	Post-Treatment (*5)	1-month Visit	3-month Visit	Every 3 month follow-up	Exit visit (*6)
TIME	Within 4 weeks prior to enrollment	Within 6 weeks prior to treatment	Within 4 weeks prior to treatment	Within 4 weeks prior to treatment	Within 4 weeks prior to treatment	Day 0	Every 2 weeks	3-5 weeks after Initial Treatment	Every 2 weeks	1 month after the last treatment	3 months after the last treatment	6, 9, 12, 15, 18, 21, 24 months after the last treatment	
Informed consent	X												
Demographics	X												
Medical history	X				X(*4)			X		X	X	X	X
Physical exam	X				X(*4)			X		X	X	X	X
Performance status	X				X(*4)			X		X	X	X	X
Concomitant medications	X				X(*4)			X		X	X	X	X
Dose calculation					X								
Order SIR-Spheres microspheres					X								
CBC, differential, platelets	X				X(*4)	X	X	X	X	X	X	X	X
PT, PTT, and INR	X				X			X					
Serum biochemistry (*1)	X				X(*4)	X	X	X	X	X	X	X	X
LDH	X				X(*4)	X	X	X	X	X	X	X	X
Pregnancy test (*2)	X				X(*4)								
Study blood drawing						X(*3)				X(*3)	X(*3)		
Liver tumor biopsy			X										
CT scan of chest, abdomen and pelvis	X				X(*4)					X	X	X	X
MRI of abdomen	X				X(*4)						X	X	X
PET scan					X						X	X	X
Volumetric measurement					X								
Hepatic angiogram				X		X		X					
Tc-99 MAA study				X									
Treatment with SIR-Spheres microspheres						X		X					
Toxicities & adverse events					X(*4)	X	X	X	X	X	X	X	X

*1: Comprehensive metabolic panel including total bilirubin, SGOT (AST), SGPT (ALT), alkaline phosphatase, albumin, creatinine, BUN, glucose, calcium

*2: For females of childbearing potential.

*3: 100 ml blood for peripheral blood mononuclear cells, and 10 ml of blood for serum collection.

*4: Tests can be skipped if screening evaluation is performed within 4 weeks prior to scheduled treatment.

*5: If necessary.

*6: Exit visit can be skipped if follow-up visit is performed within 4 weeks.

1.0Background

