4.2 Exclusion criteria

- 4.201 Failure to meet any of the criteria set forth in section 4.1.

- 4.202 Significant shunting to the lung (>20%) identified on MAA scan.
- 4.203 Unsuccessful closure of major collateral blood flows from the hepatic artery to non-targeted organs such as the GI tract. Small collaterals that are considered to be safe for Sir-Sphere® treatment by interventional radiologists and radiation oncologists are eligible.
- 4.204 A solitary liver metastasis that is amenable to surgical removal for potential cure.
- 4.205 Presence of symptomatic liver failure including ascites and hepatic encephalopathy.
- 4.206 Presence of life-limiting extra-hepatic metastasis that requires a systemic treatment within 3 months. Patients with extra-hepatic metastasis that can be controlled with a loco-regional treatment are eligible.
- 4.207 Presence of untreated brain metastases. If patients have had previous treatment for brain metastasis, an MRI or CT scan of the brain must confirm the stabilization of the brain metastasis for more than 4 weeks.
- 4.208 Occlusion of the main portal vein, or inadequate collateral flow around an occluded branch of the portal vein as determined by angiography.
- 4.209 Presence of uncontrolled hypertension or congestive heart failure, or acute myocardial infarction within 6 months of entry.
- 4.210 Presence of any other medical complications that imply a survival of less than six months.
- 4.211 Uncontrolled severe bleeding tendency or active GI bleeding.
- 4.212 Significant allergic reaction to iodinated contrast.

- 4.213 Systemic chemotherapy within 2 weeks prior to study entry (signing consent form).
- 4.214 Previous radiation treatment that includes the liver in the main radiation field.
- 4.215 Pregnancy or breast-feeding women.
- 4.216 Biliary obstruction, biliary stent, or prior biliary surgery including sphincterotomy but excluding cholecystectomy.
- 4.217 Previous treatment with isolated hepatic perfusion
- 4.218 Children under the age of 18

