5.4 Radioactive microsphere treatment

Within 4 weeks after the flow study, selective internal radiation therapy (SIRT) using yttrium-90 SIR-Spheres® microspheres (radiosphere treatment) will be performed. Due to multiple, bilobar metastases, both right and left hepatic lobes need to be treated in the majority of patients. The goal of therapy is to treat the tumor bearing liver in 2 sessions. Treatments are preferentially done in a lobar fashion. In the setting of complex anatomy, fractionated whole liver therapy is used as an alternative. In general, the delivery of radioactive microspheres will require two sequential unilobar treatments separated by a period of 4 ± 1 weeks. The lobe to be treated first will be determined by the treating physicians. The radiosphere dose for each hepatic lobe will be determined based on the tumor volume in individual lobes.

In patients whose hepatic artery does not allow two separate sequential unilobar treatments, whole liver treatment via the proper hepatic artery may be performed if no extrahepatic arteries are identified distal to the catheter site intended for radioactive microsphere delivery. The dose will be delivered in two fractionated doses separated by 4 ± 1 weeks (fractionated whole liver).

If a prior hepatectomy has been performed leaving a single lobe for treatment, or if metastatic disease is confined to a single lobe, the entire dose will be delivered in a single session to the affected lobe.

Treatment will be administered on an outpatient basis with overnight, 23-hour observation permitted at the investigator's discretion. Patients will receive the supportive care as described in Section 7.

Approximately 100ml of blood specimens will be obtained for Peripheral Blood Mononuclear Cell (PBMC) collection prior to radiosphere treatment. Additionally, 10 ml of blood specimens will be obtained for serum collection prior to, and 1 hour after radiosphere treatment.

Blood tests including CBC with differential, comprehensive metabolic panel including total

bilirubin, SGOT (AST), SGPT (ALT), LDH, alkaline phosphatase, albumin, creatinine, BUN, glucose, calcium, and LDH will be ordered every 2 weeks for one month, then every month for three months to monitor treatment-related toxicity.

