8.5 Exposure in Utero

There are no studies on the safety and effectiveness of SIR-Spheres® microspheres in pregnant women, nursing mothers or children. Women of childbearing age requiring SIR-Spheres®

microspheres should be treated when non-pregnancy can be ascertained. Safety in pregnancy and childhood has not been established and SIR-Spheres® microspheres should not be implanted into these patients.

The patient may emit low levels of radiation for several weeks, therefore care must be taken with pregnant women and children in close proximity to the patient.

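### The schedule has no pregnancy test at or between the two microsphere sessions, so the latest result can be 4 weeks old at session 1 and 9 weeks old at session 2, which sits poorly with section 8.5

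*Combined protocol and SAP*

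**What the plan says.** Section 4.2, item 4.215, excludes "Pregnancy or breast-feeding women". Section 8.5 (Exposure in Utero) says that women of childbearing age "should be treated when non-pregnancy can be ascertained". It adds that "Safety in pregnancy and childhood has not been established" and that the device should not be implanted in such patients.

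The means of checking is the pregnancy test row of the schedule table in the Protocol Summary, which footnote *2 limits as follows: "For females of childbearing potential". The row has two entries, one at screening and one at pretreatment assessment. The second carries footnote *4: "Tests can be skipped if screening evaluation is performed within 4 weeks prior to scheduled treatment". The Initial Treatment and Second Treatment cells are empty. Sections 5.1, 5.2 and 5.4 name no pregnancy test before either session.

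Section 5.4 describes the general plan as "two sequential unilobar treatments separated by a period of 4" weeks, plus or minus 1. The table gives the same interval as 3 to 5 weeks. Section 3.0 allows session 2 to be held for grade 3 toxicity for at most 6 weeks.

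**The concern.** Section 8.5 is about treatment and implantation, not only about entry to the study. With two sessions there are two implantations and two separate radiation exposures: section 8.1 gives a half-life of 64.1 hours, with 94% of the radiation delivered in 11 days. A negative test before session 1 says nothing about a conception between the sessions.

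The table offers no later test. A woman who conceives after her last test could therefore receive a permanent yttrium-90 implant at a site that has followed the schedule exactly, although the protocol says that the device should not be implanted in pregnancy. The event would be rare, but the consequence could not be undone.

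**Working it through.** The plan states no figure for the age of the test at treatment, so there is none to reproduce. The check is a reading of the table by column, followed by addition of the stated windows.

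**Inputs**
- Pretreatment assessment: 0 to 4 weeks before treatment (schedule table, time row).
- Waiver: the pretreatment test may be skipped if screening was 0 to 4 weeks before scheduled treatment (footnote *4).
- Interval from session 1 to session 2: 3 to 5 weeks (schedule table; section 5.4).
- Toxicity hold before session 2: at most 6 weeks, starting point not stated (section 3.0).

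**Age of the latest test at session 1**
- Pretreatment test done: 0 to 4 weeks.
- Pretreatment test waived: the screening test is the only one, 0 to 4 weeks old.
- Screening more than 4 weeks before treatment: the waiver does not apply and the pretreatment test is due.
- The maximum is 4 weeks on every route.

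**Age of the latest test at session 2** (age at session 1 plus the interval)
- Minimum: 0 + 3 = 3 weeks.
- Maximum: 4 + 5 = 9 weeks.
- Maximum with a hold, if the 6 weeks run from session 1: 4 + 6 = 10 weeks.
- Maximum with a hold, if the 6 weeks run from the latest planned date of session 2: 4 + 5 + 6 = 15 weeks.

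The last two lines rest on assumed starting points for the hold.

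**Comparison with other rows of the same table**

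| Row | Pretreatment assessment | Initial Treatment | Second Treatment |
|---|---|---|---|
| CBC | X, waivable | X | X |
| Serum biochemistry | X, waivable | X | X |
| LDH | X, waivable | X | X |
| PT, PTT, INR | X, not waivable | none | X |
| Pregnancy test | X, waivable | none | none |

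Of these rows, the pregnancy test is the only one that is both waivable before session 1 and not repeated at session 2.

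**The case against.** Several points on the other side are sound, and they limit what can be claimed.

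- **Section 8.5 sets no interval.** A reader might infer that it mandates a test at each session. It does not: it says should, and it names no test, interval or per-session check. How recent a result must be is a judgment, so no stated interval is contradicted.
- **Item 4.215 is an entry exclusion.** A reader might infer that it must be checked again before session 2. Nothing in the protocol says so. The argument for session 2 rests on section 8.5.
- **Footnote *4 does not cause the 4-week maximum.** The pretreatment window is itself 4 weeks, so deleting the footnote would leave that maximum unchanged. What the footnote does is let the screening test be the only one. It has no bearing on the empty cell at session 2.
- **There is a partial check.** History and physical examination are marked at Second Treatment without a waiver, and section 8.5 still binds the treating physician. It would go too far to say that a pregnancy must be missed. But the protocol chose a test as its means of checking, and these items do not replace one.
- **Few patients are exposed.** The plan is for 48 patients. In the institution's own series of 12 there were 7 women, and ages ran from 48 to 81 (section 1.8). Session 2 is given only if necessary (footnote *5), and disease confined to one lobe is treated in a single session. Against that, entry is open from age 18, footnote *2 provides for women of childbearing potential, and two sessions are the general plan.
- **Some material cannot be seen.** Sections 4.1 and 4.2 contain no contraception requirement, but the consent pages and the User Manual (Appendix 1) are not available and may contain one. No conclusion is drawn from its absence here.

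What remains is that the table provides no test after the one preceding session 1.

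**Conclusion.** The schedule and section 8.5 do not fit together, most clearly for session 2. The latest test may be up to 4 weeks old at the first implantation and 3 to 9 weeks old at the second. With a toxicity hold the maximum becomes 10 or 15 weeks, depending on an assumed start of the hold. Between the sessions the table contains no test that would support ascertaining non-pregnancy, although it repeats other laboratory tests at session 2.

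This is a patient-safety gap with a low expected frequency and a serious possible consequence. It does not affect the sample size, the two-stage rule, the error rates or any endpoint. The conclusion rests on the pregnancy row as it stands in the schedule table, and on the absence of any pregnancy test in sections 5.1, 5.2 and 5.4.

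**What to change.** Reconcile the pregnancy test row and footnote *4 with section 8.5, and with the entry exclusion 4.215, so that the schedule supports ascertaining non-pregnancy before each implantation, including session 2 and any session 2 delayed by toxicity. The type and timing of the test are for the sponsor and investigator to set. A change to footnote *4 alone would not be enough, because it would not reach session 2.

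The cost is an edit to the schedule table and a small amount of extra laboratory testing in the few patients of childbearing potential. Nothing in the statistical section needs to change.

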1.1 Uveal Melanoma

Uveal melanoma is the most common adult primary intraocular malignant tumor (1, 2). The incidence of uveal melanoma is 4.3 cases per million population, with a slightly higher rate in males (4.9 cases per million) when compared with females (3.7 cases per million). Uveal melanoma is more commonly seen in an older age group, with a progressively rising age-specific incidence rate that peaks at the age of 70 years (24.5 cases per million in males and 17.8 cases per million in females) (3).

Up to 50% of patients with posterior uveal melanoma subsequently develop systemic metastasis after the initial diagnosis and treatment (4), however, clinically evident metastatic disease at the time of initial presentation is uncommon, indicating that there is early subclinical metastasis in most cases (5). The liver is the predominant organ involved in 70% to 90% of cases with metastatic uveal melanoma (6-8) and tends to be the first manifestation of metastatic disease (8, 9). Lungs (20%), bone (16%), and skin (12%) are other sites that may be affected (9). The metastatic pattern of uveal melanoma is often distinct from that of the cutaneous form of the disease. Approximately 90% of uveal melanoma patients die with liver metastases (7). Despite achieving great accuracy in correctly diagnosing uveal melanoma in the United States (2), mortality owing to this tumor has remained unchanged over the past 3 decades (5). In general, the survival with metastatic uveal melanoma is poor, with a median survival of less than 6 months (6, 8).

Many cytogenetic investigations of primary uveal melanoma have revealed that the majority of choroidal and ciliary body melanomas are characterized by non-random alterations in chromosomes 1, 3, 6 and 8 (10). Monosomy 3 (either true or functional) and trisomy 8, partial duplication of 8q, or iso-chromosome 8q are the most frequent karyotypic abnormalities present in approximately 50% of cases (10). Recent investigation has indicated that monosomy 3 is a significant predictor of poor prognosis (11). Approximately 70% of patients with monosomy 3 in their primary tumor have died of metastases within 4 years after the initial diagnosis; whereas tumors with normal chromosome 3 status (disomy 3) rarely gave rise to metastatic disease (11). Existence of chromosome 3 abnormality in hepatic metastasis might be correlated to the outcome

of trans-arterial embolization of metastases (12).

1.2 Systemic Treatment for Metastatic Uveal Melanoma

Systemic chemotherapy has failed to show significant efficacy against metastatic uveal melanoma. Retrospective reviews from the M. D. Anderson Cancer Center and ECOG indicated that the response rates to chemotherapeutic drugs commonly used for the treatment of metastatic cutaneous/mucosal melanoma rarely induced responses in patients with uveal melanoma, especially when the liver was involved with metastatic disease (9, 13). Dacarbazine-based chemotherapies that have been used for the treatment of metastatic cutaneous melanoma are ineffective in the treatment of metastatic uveal melanoma (9, 13, 14).

Pyrhonen et al. reported superior results in a pilot study using the combination of bleomycin, Oncovin, lomustine, DTIC (BOLD) plus interferon in a small group of patients with metastatic uveal melanoma (15). This combination has been evaluated in several other clinical trials and was reported to give markedly variable response rates (15-18). The average response rate is 14%, hardly an improvement over other regimens. Neurotoxicity was observed in 13% of the patients. Severe and unpredictable pulmonary toxicity was observed occasionally (16).

The combinations of treosulfan with gemcitabine or cytosine arabinoside were shown to be active in over 70% of uveal melanoma cells tested with *ex vivo* sensitivity test (19). Based on these results, clinical trials using the treosulfan-gemcitabine combination were conducted with modest clinical benefit (20).

Dorval et al. failed to discern any objective responses to high dose IL-2 in their study of patients with metastatic uveal melanoma (21).

1.3 Surgical Treatment for Liver Metastases

Since the liver is the first and in many cases the only site of metastases in patients with uveal melanoma, local treatment aimed at controlling liver metastases holds promise in managing this otherwise highly chemo-resistant tumor. Total resection of the solitary metastasis in the liver or other sites (22, 23) offers a distinct survival advantage. We reported protracted survival with surgery for visceral metastases from uveal melanoma. However, only 9% of patients with

metastases were eligible for surgical intervention (22). The longest median survival of 22 months was observed when a complete surgical excision of the hepatic metastasis was followed by intra-arterial hepatic fotemustine or dacarbazine plus cisplatin (24).

1.4 Hepatic Intraarterial Chemotherapy for Liver Metastases

Hepatic intra-arterial chemoinfusion with an agent that has a rapid systemic clearance rate and a high hepatic extraction rate allows maximum local drug exposure. Leyvraz, et al. reported that intrahepatic chemoinfusion of Fotemustine resulted in a response rate of 40% for patients with liver metastases from uveal melanoma (25). Hepatic intra-arterial chemoinfusion with carboplatin was also used for liver metastases from uveal melanoma (26).

Isolated hepatic perfusion (IHP) has been used for liver metastases from uveal melanoma (27). A series of 22 patients with metastatic uveal melanoma confined to liver was treated at the National Cancer Institute using IHP with melphalan and TNF- α (n=11) or melphalan alone (n=11) (27). There was one treatment-related death. Among the 21 evaluable patients, there were two radiographic complete responses (9.5%) and 11 partial responses (52%). The overall median duration of response was 9 months (range 5-50 months). Recently, a special catheter system has been developed to isolate the hepatic circulation from the systemic circulation. This allows multiple cycles of chemotherapy to be delivered directly to the liver without a major operation (peripheral hepatic perfusion, PHP). A randomized phase III trial comparing PHP and the best available treatment is ongoing.

1.5 Chemoembolization of Liver Metastases

Mavligit et al. reported that hepatic artery chemoembolization with cisplatin and polyvinyl sponge achieved a 46% response rate with a median survival of 11 months (28). We subsequently conducted a phase II trial of hepatic artery chemoembolization using 1,3-bis (2-chloroethyl)-1-nitrosourea (BCNU) in combination with ethiodized oil followed by infusion of a transiently occlusive agent, gelatin sponge particles (29). A total of 29 patients were treated with chemoembolization with BCNU. Among 23 evaluable patients, one patient achieved complete response (CR), 3 patients achieved partial response (PR) and 12 patients achieved stable disease (SD). Median overall survival (OS) of the entire intent-to-treat group of patients was 5.1 months (range 0.1-27.6); for patients with CR or PR, 23.5 months (range 7.4-27.6); SD, 8.7 months (range

2.9-14.4); and progressive disease (PD), 3.3 months (range 1.6-5.6). Importantly, while control of hepatic metastases was obtained, progression was seen in extra-hepatic sites such as spine, lung, lymph nodes, and brain in more than two thirds of patients (29).

1.6 Immunoembolization of Liver Metastases

Since local chemotherapies for metastatic uveal melanoma are not uniformly successful and since even successful local chemotherapies frequently fail at extrahepatic sites, a local immunotherapy is theoretically a reasonable approach to control the liver metastases and to potentially induce a systemic antitumor immune response to prevent distant failure. Based on the above scientific rationale, our group developed a novel approach to the treatment of liver malignancy using embolization of the liver metastases with granulocyte-macrophage colony stimulating factor (GM-CSF) (immunoembolization).

In our phase I clinical study, 34 uveal melanoma patients with less than 50% involvement of the liver were treated with immunoembolization of hepatic metastases with various doses of GM-CSF (30). There were no treatment-related deaths or life-threatening events observed up to and including the 2,000 μ g dose level of GM-CSF. Among 31 evaluable patients, there were 2 complete responses (CR), 8 partial responses (PR), and 10 cases of stable disease (SD) in their hepatic metastases. The median overall survival (OS) of intent-to-treat patients was 14.4 months. Multivariate analyses indicated that female gender, high doses of GM-CSF (\geq 1,500 μ g) and regression of hepatic metastases (CR and PR) were correlated to longer OS (30).

The result of the phase I trial with immunoembolization was also compared to our institutional historical control of patients who were treated with chemoembolization using BCNU (less than 50% involvement of the liver with metastases). Compared with 19 patients who received chemoembolization, 16 patients who received high dose immunoembolization had significantly better OS (20.4 vs. 9.8 months, $P = .005$) and progression free survival in systemic (extra-hepatic) sites (PFS-S) (12.4 vs. 4.8 months, $P = .001$) (31).

